# Minimal Risk Protocol Template

## 1) Protocol Title

Enhancing Skin Cancer Early Detection and Treatment in Primary Care

## 2) Objectives

This mixed method study will evaluate whether a multicomponent education strategy improves the ability of Primary Care Providers (PCPs) to identify and triage skin cancer. This study will be deployed in two OHSU family medicine clinics: one OHSU Family medicine rural-based clinic and one urban underserved Federally Qualified Health Center (FQHC) clinic. Baseline data and those not participating in the training will serve as controls.

## 3) Background

Cutaneous melanoma (CM) is a potentially life-threatening form of skin cancer that is increasing in incidence. In the last three decades, incidence rates have more than tripled, and CM currently stands as the fifth most common invasive cancer in the United States. According to estimates by the American Cancer Society (ACS), there will be nearly 100,000 new cases of CM and about 7,650 deaths due to melanoma in 2022 alone. The ACS expects that 1,640 of these new cases will occur in Oregon, which consistently ranks among the top ten states in the nation for CM incidence. Unlike other common malignancies, melanoma is most often evident directly on the skin's surface, which lends the opportunity to improve early recognition with the goal of decreasing mortality.

If diagnosed early, both CM and other types of skin cancers are often curable. For distant metastatic disease, however, the prognosis is substantially worse. Stage I CM disease carries a five-year survival rate of 99%. For stage IV CM, however, the five-year survival rate drops to 30%. In addition to higher mortality rates, late-stage disease is also associated with increased morbidity and increased health care costs. For example, late-stage tumors require wider excision margins, sentinel lymph node sampling, increased imaging surveillance, and may necessitate the use of expensive and potentially toxic therapies in the treatment or adjuvant setting.

The early detection of melanoma through simple, noninvasive screening practices has a considerable potential to reduce the burden of this disease. In Oregon, there are few dermatologists in the areas of highest incidence, so PCPs are in a unique position to recognize and treat or triage skin cancers. However, PCPs have identified barriers to their ability to diagnose skin cancer, including knowledge gaps, paucity of time and lack of clinical workflows for routine screening and electronic health record (EHR) support tools to facilitate screening. Dermoscopy (using a device with polarized light and magnification to visualize underlying skin structures) and EHR tools designed to facilitate skin screenings can help overcome these barriers but are rarely used in PCP settings. We hypothesize that providing PCPs with the appropriate training and tools to screen for and recognize melanoma will facilitate diagnosis of more skin cancers at earlier

stages. Our team has already developed and demonstrated the efficacy of a PCP education intervention (Melanoma Toolkit for Early Detection, MTED) and is poised to deploy this toolkit in the pilot study outlined in this protocol.

## 4) Study Design

This study is a mixed method pilot study to determine whether multicomponent education module improves the ability of Primary Care Providers (PCPs) to identify and triage skin cancer. The main independent variable is the multicomponent education for clinicians. This is primarily a feasibility study to evaluate the engagement and uptake of the training and change in skin cancer screening behavior on the part of clinical teams. We hypothesize that exposure to the intervention will increase clinician knowledge, increase the use of a SKLIP dermoscopy device to facilitate capture of high-resolution dermoscopy images, and increase screening for skin cancer.

Outcomes:

- Uptake of the training and performance of skin cancer screening processes measured by proportion of clinicians invited to participate in the educational intervention that complete the training modules; use of the Epic smart tool and dotphrases.
- Clinical knowledge measured through pre- and post-tests implemented during live (in-person or virtual) training.
- Use of the risk assessment tool measured through EHR data.
- Identification of suspicious lesions measured through EHR data.

We hypothesize that the multicomponent education strategy will result in the diagnosis of more skin cancers at earlier stages. Primary endpoints of the study include the pre- and post-intervention: number of melanomas biopsied, mean and median Breslow depth of melanomas biopsied, number of other malignant skin tumors biopsied, total number of referrals to dermatology, number of referrals to dermatology for concerning moles, and number of OHSU PCPs who access the Melanoma Toolkit for Early Detection (MTED), an online Continuing Medical Education training. There will be two comparison groups: OHSU PCPs receiving the intervention, OHSU PCPs not exposed to the intervention.

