**b) Inclusion and Exclusion Criteria**

Two OHSU primary care clinics will be assigned to receive exposure to the melanoma early detection intervention. Baseline data and clinicians at the two clinics who do not receive the intervention will serve as study comparators.

We will be using secondary EHR data from the study clinics. Biopsy and referral data will be extracted from EHR from patients within these two primary care clinics who were screened, referred, biopsied for potential skin cancer and/or diagnosed with melanoma. Data from all other patients seen in these clinics during the time period will be included for comparison. These data will be electronic health record (EHR) data from patients between the ages of 18 and 110 with an encounter in one of the study clinics. A subset of this data will undergo a chart review to affirm use of specific devices to photograph lesions and free text biopsy results and/or interpretation.

We may observe all in-person trainings. There are no inclusion/exclusion criteria for training observation. All training participants will be 18 years or older and are required to speak English during the training and in their occupations.

Qualitative interviews will be conducted with clinicians who receive the intervention. These individuals are all aged 18 years or older and all practice members speak English. No patients will be interviewed for this research.

Exclusion criteria: No one will be intentionally excluded.

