## 6) Study Procedures & Schedule of Events

The multi-component educational intervention includes the following:

Training:

*Group Training:*

Group training sessions will consist of an initial training and an one hour follow up refresher training on how to use the SKILP device and identifying Melanoma. The in-person trainings are designed as lunch and learn sessions. The initial training will include how to use the MTED, how to use a SKILP dermoscopy device, how to use the Epic health maintenance reminder tool to document a high-risk patient, and how to triage. We will support workflow restructure to involve use of Epic tools, SKILP devices, etc. but are unable to assess changes to workflow itself. PCPs will receive education on how to use a collection of skin cancer-specific SmartPhrases in Epic. These SmartPhrases contain resources such as a melanoma risk stratification tool, skin cancer after visit summary, and templates for biopsies and skin exams. An accompanying PowerPoint document explains how to access and use the SmartPhrases, as well as provides instructions on how to satisfy billing codes and health maintenance reminders. The training is tailored to PCPs but may be delivered to the entire healthcare team (nursing staff and medical assistants) to facilitate implementation.

The follow up refresher training will follow the same format as the initial training and will contain similar content as the initial training (See Dermoscopic Red Flags of Melanoma Powerpoint in Supplemental Materials).

Live trainings may be in-person or virtual, but will not be recorded. We will use a sign-in sheet to collect names and email addresses of those who attended the in-person trainings so that we may follow up with them and provide a link to the online portion of the trainings and to measure expose of the training.

Lunches will be provided at all group training sessions, along with SKILP devices at the intial training and educational materials. Pre- and post-training tests will be given during the initial in-person training session to measure uptake of the training. These tests will be distributed through an email about the upcoming training (see supplemental materials) and a QR code that

participants can access through their phones or laptops during the training. A pre-recorded version of the trainings will also be available to accommodate busy schedules.

*Refresher trainings:*

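### Use of the Epic tools that the training teaches also stands for screening performance, so documented screening can rise with no extra skin exams

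*Protocol*

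**What the plan says.** Protocol section 4 gives as one purpose of the study to evaluate "change in skin cancer screening behavior on the part of clinical teams", and hypothesises that screening will increase. The first outcome listed there is "Uptake of the training and performance of skin cancer screening processes measured by" the proportion of invited clinicians who "complete the training modules; use of the Epic smart tool and dotphrases".

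Section 6 (Group Training) describes what is taught: "PCPs will receive education on how to use a collection of skin cancer-specific SmartPhrases in Epic". Their contents include a melanoma risk stratification tool and "templates for biopsies and skin exams". The initial session also covers "how to use the Epic health maintenance reminder tool to document a high-risk patient", and the accompanying slides explain how to meet billing codes and reminders. The online toolkit in the same section supplies the Epic tools again.

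Section 8 compares screening, among other outcomes, between trained clinicians and untrained clinicians at the same sites, from baseline to post-intervention. Table 1 lists whether screening was performed separately from use of the screening tool and of the dotphrase. The source given is the EHR and chart review, but there is no rule for ascertaining the field. On chart review, section 5b says: "A subset of this data will undergo a chart review to affirm use of specific devices to photograph lesions and free text biopsy results".

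**The concern.** The first outcome joins two ideas, uptake and screening performance, and gives two measures. Module completion says nothing about screening, so use of the tools carries that part alone. Those tools are part of the intervention. Training therefore changes how an exam is recorded, whether or not it changes how many patients are examined.

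A baseline period or an untrained comparator removes a bias that is common to the groups or constant over time. This one arises mainly among trained clinicians after training, so the group-by-period contrast counts it as effect. At stake is the conclusion on one of the study's hypotheses: a rise in structured documentation could be reported as a change in screening behaviour.

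**Working it through.** **Step 1. Does the text make the measure part of the intervention?** I read the dotphrases in section 4 as the SmartPhrases in section 6. Section 4 names use of the Epic smart tool and dotphrases as a measure. Section 6 teaches the SmartPhrases, including skin-exam templates, and the reminder tool. The overlap is direct.

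**Step 2. Does another stated procedure separate exams from their recording?** The chart review purposes in sections 5a, 5b and 6 are device photographs and biopsy results. None of these sections says that it checks whether a skin exam took place. The Table 1 screening field could do so, but it is undefined. If it were built from codes or reminders it would have the same weakness, because both are taught.

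**Step 3. Does the comparison cancel the artefact?** Let *e* be the true exam rate, the same in both groups and periods, and *c* the share of exams recorded with the tools (capture). The documented rate is *e* × *c*. The ratio of post/pre ratios, trained over untrained, is

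(*e*·c_T,post / *e*·c_T,pre) ÷ (*e*·c_U,post / *e*·c_U,pre).

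The exam rate cancels. If capture is flat in untrained clinicians, what remains is c_T,post / c_T,pre, although no more patients are examined. On the difference scale the artefact is *e* × (c_T,post − c_T,pre).

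**Step 4. Illustrative size.** The documents give no exam or capture rate, so there is no figure of theirs to reproduce. All values below are assumptions: *e* = 10%, and flat capture in untrained clinicians.

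| Capture in trained clinicians, pre → post | Documented per 1000 patients, pre → post | Spurious difference per 1000 | Spurious ratio |
|---|---|---|---|
| 50% → 60% | 50 → 60 | 10 | 60/50 = 1.2 |
| 30% → 50% | 30 → 50 | 20 | 50/30 = 1.67 |
| 10% → 20% | 10 → 20 | 10 | 20/10 = 2.0 |
| 10% → 50% | 10 → 50 | 40 | 50/10 = 5.0 |

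The ratios do not depend on *e*; the differences scale with it.

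**Step 5. Chance of a false significant result.** The printed totals in Tables 2 and 3 are 6251 + 4737 = 10,988 and 6670 + 5012 = 11,682 patients, together 22,670. Assume that half, 11,335, are seen by trained clinicians in each period, and compare the two documented proportions at two-sided 5%. With an assumed design effect of 10, the chance of significance for the four rows is about 18%, 68%, 50% and 100%. With a design effect of 20 it is about 11%, 40%, 28% and 98%. This is the pre-post contrast within trained clinicians. The group-by-period interaction also carries the sampling error of the untrained group, so its chances would be lower.

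**The case against.** The strongest reply is that the outcome is mainly one of uptake. Section 4 calls this primarily a feasibility study, and use of taught tools is a legitimate adoption measure in a pilot. Table 1 keeps screening performed apart from tool and dotphrase use, and nothing says that the screening compared in section 8 is dotphrase use. Much of this stands: tool use is a sound uptake measure. But section 4 is the only place that says how screening performance is measured, and the Table 1 field has no definition to put in its place.

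Three stronger readings are tempting and not supported.

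- *A positive screening result is nearly certain.* This needs roughly zero capture in three of the four cells. With 10% of patients examined and 25% to 75% of exams captured in the fourth cell, the artefact would be 2.5 to 7.5 percentage points. The Background section says that EHR tools for skin screening are seldom used in primary care, which makes low baseline capture plausible but does not establish zero. Untrained clinicians share the two sites, training may extend to the whole care team, and section 6 supports workflow change around the Epic tools. Spillover would shrink the artefact.
- *The trial's main results are compromised.* No primary endpoint in section 4 is defined by dotphrase use. The final SAP describes e-consults, referrals and biopsies, tests knowledge scores, and models referral outcomes. It names no screening or tool-use outcome.
- *The planned chart review can easily be turned into the remedy.* At a 10% exam rate and without clustering, the variance of a difference-in-differences with *n* charts per cell is 4 × 0.09/*n*. A 95% interval of ±5 points needs *n* = 0.36 × (1.96/0.05)² ≈ 553 per cell, about 2,200 charts. For ±2.5 points it is about 8,850. Section 5a plans chart review only for an unspecified subset.

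**Conclusion.** The point holds within limits. As section 4 is written, documented screening can rise in trained clinicians after training with no additional skin exams, and the comparison in section 8 does not remove that.

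How far it would rise is unknown. Spurious ratios of 1.2 to 5.0 follow from assumed capture and from flat capture in untrained clinicians. They show that the artefact can be anything from modest to large; they do not estimate it. The same applies to the chances of significance, which run from 11% to about 100% over the assumed scenarios and design effects.

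The problem affects the screening-process outcome and the protocol's screening comparison. It gives no reason to doubt the primary endpoints or the final SAP models.

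**What to change.** 1. In section 4, separate the two ideas. Report module completion and use of the Epic smart tool and dotphrases as training uptake only.
2. Base any statement about change in screening on the existing Table 1 field for screening performed. Define it as any documented skin exam, structured or free text, independent of the taught tools, codes and reminders. Apply the same definition to trained and untrained clinicians in both periods.
3. If the field cannot be ascertained in that way, make no claim of increased screening from tool use. The SAP is dated March 2025 and written in the past tense, so this may be the step that still applies to reporting.

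Steps 1 and 3 cost only wording. Step 2 costs a definition and the work of finding free-text exams in the record.

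A chart check of a modest sample from the four group-by-period cells is optional support only. It would be imprecise, as the chart counts above show. It would be hard to blind, because template text reveals exposure. It also could not remove any effect of training on whether an exam is written down at all.

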## 5) Study Population

### a) Number of Subjects

This study will be conducted at two primary care clinics. Within these two clinics, there are approximately 80 clinicians (e.g. MD, NP, PA, DO, APP).

We will invite all advanced practice providers (MD, NP, PA, DO) at these two clinic sites to participate in the multicomponent educational intervention, up to 40 clinicians per site. These clinicians will take part in the surveys imbedded in the Toolkit, surveys pre-and post-training, and live (in-person/virtual) trainings. Thus, we will recruit approximately 40 clinicians within the 2 clinics for the active intervention.

We will observe the in-person trainings and take detailed fieldnotes. We expect approximately 40 clinicians will participate in each training.

We will interview approximately 5-10 members per site within the clinic.

We will extract EHR data collected from patients from within these two clinics for the year prior and for 1-year post training implementation (2/1/2022-9/30/2024). We estimate up to 200 individuals with biopsies per year, per clinic. For a subset of patients, we will conduct a chart review to affirm use of specific devices to photograph lesions and biopsy results that are not readily ascertainable from EHR data alone.

**b) Inclusion and Exclusion Criteria**

Two OHSU primary care clinics will be assigned to receive exposure to the melanoma early detection intervention. Baseline data and clinicians at the two clinics who do not receive the intervention will serve as study comparators.

We will be using secondary EHR data from the study clinics. Biopsy and referral data will be extracted from EHR from patients within these two primary care clinics who were screened, referred, biopsied for potential skin cancer and/or diagnosed with melanoma. Data from all other patients seen in these clinics during the time period will be included for comparison. These data will be electronic health record (EHR) data from patients between the ages of 18 and 110 with an encounter in one of the study clinics. A subset of this data will undergo a chart review to affirm use of specific devices to photograph lesions and free text biopsy results and/or interpretation.

We may observe all in-person trainings. There are no inclusion/exclusion criteria for training observation. All training participants will be 18 years or older and are required to speak English during the training and in their occupations.

Qualitative interviews will be conducted with clinicians who receive the intervention. These individuals are all aged 18 years or older and all practice members speak English. No patients will be interviewed for this research.

Exclusion criteria: No one will be intentionally excluded.

**c) Vulnerable Populations**

This study will not target vulnerable populations, but they may be included in the EHR data. EHR data may include patients under 18, those who may be pregnant or decisionally impaired.

**d) Setting**

This study will be conducted at OHSU and deployed at two clinics: one OHSU Family medicine rural based clinic and one urban underserved FQHC clinic. Study information will be collected using EPIC data fields to assess biopsy rates, uptake of risk assessment and health maintenance (HM) reminders and use of e consult and formal consultation. Qualitative data will be collected

using semi-structured qualitative interviews via in-person, phone or video calls. We will also conduct and observe in-person trainings.

The population health team at OHSU will pull EHR data from OHSU primary care clinics. They will provide a de-identified dataset to OHSU researchers for analysis. No OHSU data will leave OHSU.

**e) Recruitment Methods**

Study staff will submit an inquiry for research engagement per the Department of Family Medicine's current Standard Operating Procedure. DFM research leadership and clinic leadership will confirm the participation of each clinical site. Then, with clinic leadership support, advanced providers from each site will be invited to participate in the multicomponent educational intervention.

We will email leaders at each of the sites and ask for permission to observe the trainings and take fieldnotes. A reminder invite to the in-person training will be shared with clinic leadership, and will be emailed to the participating clinic members (see recruitment materials). This email will remind participating clinic members of the upcoming training and include and a copy of the information sheet. During the live training, we will ask participants for their email addresses so that we may remind them to complete the training post-test and to invite them to complete the online portion of the trainings. (See supplemental materials).

Patients are not being directly recruited to this study however, patient level EHR data will be used to evaluate the impact of the intervention as outlined in the primary endpoints above.

We will invite and potentially interview all clinicians but will stop once saturation is reached and no new information is being gleaned. In exchange for participation in the one hour interview, clinician member participants will receive a \$100 Amazon gift card.

**f) Consent Process**

As the risks to the clinic staff are minimal, we will request IRB approval to provide study information sheets. Clinicians who participate in the intervention will receive a study information sheet describing their participation in the in-person training, online learning modules (MTED), the possibility of participating in qualitative interviews, and how data will be used to answer study questions.

For the qualitative training observations, we will ask for permission to join the trainings and take field notes. This study poses a minimal risk to participants, and as such, a formal consent process is not required for observation.

For the qualitative interviews, we request a waiver of written consent. This request is justified, since if signed, the signature would be the only thing that would identify the interviewee in study records. We will avoid using names during the interviews. If names are used, they will be scrubbed from the transcript during the transcribing process. The research team will make clear that the interviewee does not need to participate in the interview and there are no repercussions for saying no. Prior to an interview, practice members will receive an Information Sheet stating the purpose of the study and explaining their rights as a participant in the study. The study team will answer any questions about the study, obtain verbal consent, and ask

permission to record the interview. If a participant agrees to be interviewed but not audio-recorded the interviewer will take notes during the interview and write them up shortly afterwards. Participants will also be instructed that they can request the audio recording to be stopped at any point during the interview.

We are requesting a waiver of authorization and consent for secondary analysis of EHR data in this research, as patients are not actively recruited. We believe this study meets the necessary requirement for a waiver of authorization and consent as: 1) the research involves no more than minimal risk to the subjects; 2) the waiver or alteration will not adversely affect the rights and welfare of the subjects as it involves no more than a minimal risk of loss of confidentiality; and, 3) the research could not practicably be carried out without the waiver or alteration because it would not be possible to consent the number of patients whose EHR records are needed to answer the study question.

